3.3.2 Study periods

For reporting purposes, the Evaluation Period will last from the date of first dose in EP0132 until the FV inclusive, or from the date of first dose in EP0132 until the EDV inclusive for study participants who prematurely discontinue the study. The Evaluation Period may be truncated at the Month 24 YEV for the reporting of the absence seizure freedom based on seizure data (diary and EEG). It is expected that the first dose in EP0132 will be taken in the evening of the EV. For

participants who complete the study at the FV, the Overall Period will include the Evaluation Period only. Otherwise, for participants who are not required to down-titrate as a dose of 1mg/kg/day (50mg/day for study participants with body weight $>50\text{kg}$) is reached at the FV or EDV, the Overall Period will include the Evaluation Period and Safety Period. Otherwise, the Overall Period will include the Evaluation Period, Down-Titration Period and Safety Period.

For study participants who discontinue BRV treatment following the EDV or FV and a dose of $>1\text{mg/kg/day}$ ($>50\text{mg/day}$ for study participants with body weight $\geq 50\text{kg}$) is reached at the EDV or FV respectively, the BRV dose will be reduced by a maximum of half the dose every week for a maximum of 4 weeks until a dose of 1mg/kg/day (50mg/day for study participants with body weight $>50\text{kg}$) is reached (Down-Titration Period). A DTV will be performed at the end of the Down-Titration Period, and study drug will be discontinued at the DTV. Otherwise, for study participants who will discontinue BRV treatment following the EDV or FV and a dose of 1mg/kg/day (50mg/day for study participants with body weight $>50\text{kg}$) is reached at the EDV or FV respectively, down titration will not be applicable.

After 2 weeks free of study drug (Safety Period), study participants will complete the SV.

The definitions of the Evaluation, Down-Titration, Safety Follow-up, and Overall Periods are provided in [Table 3-2](#). Adverse events are assigned to a study period based on the date of onset. All other measurements are assigned based on the date of assessment.

Table 3-2: Definition of study periods

Period	Definition	Algorithmic rule

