Evaluation Period	From the date of first dose in EP0132 inclusive until: 
• FV inclusive for participants who complete the study, or• EDV inclusive for participants who discontinue the study early	Day of first dose in EP0132 eCRF date inclusive to 
• If the participant completed the study: day of FV eCRF date inclusive;• Else if the participant attended the EDV: day of EDV eCRF date inclusive;• Else if the participant did not attend one of these visits (eg, is lost to follow up): day of last study medication as recorded on the Study Termination eCRF inclusive;• Else if the participant died: the date of death inclusive.
Down-Titration Period	
• From the day after the FV inclusive for study participants who complete the study and	
• If the participant completed the study and subsequently down-titrated: day after the FV eCRF date inclusive;

Table 3-2: Definition of study periods

Period	Definition	Algorithmic rule
	
subsequently discontinue BRV, or
 
From the day after the EDV inclusive for study participants who discontinue the study early and subsequently discontinue BRV 
to
 
the DTV inclusive.
	
If the participant attended the EDV: day after the EDV eCRF date inclusiveIf the participant attended the DTV: day of DTV eCRF date inclusive;Else if the participant did not attend the DTV: day of last study medication as recorded on the Study Termination eCRF inclusive;Else if the participant died: the date of death inclusive.

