3.13.4 Absence seizure freedom based on diary (including dropouts)

The endpoint of absence seizure freedom based on diary will be assessed at 3-month time intervals within the Evaluation Period, as defined in [Table 3-3](#), and over the entire Evaluation Period. The Evaluation Period may include any additional diary entries collected from the end of the Months 22 to 24 period up to the Month 24 YEV where the Evaluation Period is truncated for participants who reach the Month 24 YEV.

In each 3-month period (or Evaluation Period), a study participant is defined as absence seizure free if they meet all the following criteria:

1. The study participant completed their seizure diary on at least 80% of days within the relevant period. Seizure diary is defined as completed if “Diary completed” is answered “Yes” for each applicable day in the period. If “Diary completed” is answered “No” or the diary record is missing it will be defined as not completed for that day.
2. No absence seizures are reported in the seizure diaries in the relevant period
3. No concomitant use of any AEDs, including benzodiazepines during the relevant period

Specific algorithmic rules for each of the above criteria are defined as follows:

Criterion 1: Seizure diary data is reported on the Seizure Classification eCRF for at least 80% of the days within the relevant period

Criterion 2: No diary records on the Seizure Classification eCRF within the relevant period are reported with answer “Yes” to the question “Did Any Absence Seizures occur?”

Criterion 3: No records of any concomitant AED, including benzodiazepines, usage on the Concomitant Medications eCRF within the relevant period

Note that Criterion 2 and 3 will only be assessed if Criterion 1 is met. In each 3-month period (or Evaluation Period), if the study participant does not meet all the criteria for absence seizure freedom they will be regarded as not absence seizure free.

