If a study participant discontinues the study during a 3-month period then Criterion 1 will be checked based on the full 3-month period and if met, the participant will be assessed for absence seizure freedom in the period of discontinuation. If Criterion 1 is not met, absence seizure freedom status will be imputed as not absence seizure free for the period of discontinuation and all subsequent 3-month periods, ending at Months 22 to 24. Study participants who discontinue the study early will still be included in the analysis conducted on the Evaluation Period.

If a study participant has a FV during a 3-month period then Criterion 1 will be checked based on the full 3-month period and if met, the participant will be assessed for absence seizure freedom in the period of the FV. If Criterion 1 is not met, the participant will not be included in the summary for that period and all subsequent 3-month periods, ending at Months 22 to 24. Study participants who have a FV prior to the scheduled Month 24 YEV will still be included in the analysis conducted on the Evaluation Period.

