3.13.5 Absence seizure freedom based on diary (excluding dropouts)

The endpoint of absence seizure freedom based on diary will be assessed at 3-month time intervals within the Evaluation Period, as defined in [Table 3-3](#), and over the entire Evaluation Period. The Evaluation Period may include any additional diary entries collected from the end of the 3-month Months 22 to 24 period up to the Month 24 YEV where the Evaluation Period is truncated for participants who reach the Month 24 YEV.

The derivation will be the same as [Section 3.13.4](#) apart from if a study participant discontinues or completes the study during a 3-month period then Criterion 1 will be checked and if met, the participant will be assessed for absence seizure freedom in the period of discontinuation. If they do not meet Criterion 1 during the period of study discontinuation the study participant will not be included in the analysis for that period. Additionally, they will not be included in the analysis of any period subsequent to that of study discontinuation or completion. If a study participant discontinues the study at any time before the scheduled Month 24 YEV, they will not be included in the analysis conducted on the Evaluation Period. However, if a study participant has a FV prior to the scheduled Month 24 YEV, they will be included in the analysis conducted on the Evaluation Period.

3.13.6 Absence seizure freedom based on diary with modified criterion based on seizure diary completion (including dropouts)

The endpoint of absence seizure freedom based on diary with modified criterion based on seizure diary completion (including dropouts) will be derived in the same way as the endpoint defined in [Section 3.13.4](#), however Criterion 1 will be updated to require a minimum of 50% of days of seizure diary completion within the relevant period.

3.13.7 Absence seizure freedom based on diary with modified criterion based on seizure diary completion (excluding dropouts)

The endpoint of absence seizure freedom based on diary with modified criterion based on seizure diary completion (excluding dropouts) will be assessed at 3-month time intervals within the Evaluation Period, as defined in [Table 3-3](#), and over the entire Evaluation Period. The Evaluation Period may include any additional diary entries collected from the end of the Months 22 to 24 period up to the Month 24 YEV where the Evaluation Period is truncated for participants who reach the Month 24 YEV.

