4 STATISTICAL/ANALYTICAL ISSUES

4.1 Handling of dropouts or missing data

4.1.1 Missing data

4.1.1.1 Seizure data

Six analyses of the proportion of study participants with absence seizure freedom will be conducted: 2 using 1-hour EEG, and 4 using seizure diaries. These analyses will be conducted as described in [Sections 3.13.2, 3.13.3, 3.13.4, 3.13.5, 3.13.6, and 3.13.7](#) respectively; for each of EEG, seizure diary, and seizure diary with modified criterion there is one analysis with imputation of non-response truncated at 24 months for participants who discontinue the study early, and one with no imputation of non-response for participants who discontinue the study early. There will be no missing data for the imputation analysis, as a study participant who does not meet all the criteria for absence seizure freedom will be regarded as not absence seizure free.

The proportion of 1-hour EEGs without absence seizure freedom will be artificially increased if some criteria have not been completed, hence every effort should be made to follow-up on missing criteria. All 1-hour EEGs with missing criteria should be discussed at DEMs, in order to determine the current stage of data management (ie, queried, response, resolution), the reason for the missingness (if available) and if additional sensitivity analysis are required. Also, note that 1-hour EEG listings will include information on which criteria have been met, not met, and are missing.

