8.1.3 Absence seizure freedom based on diary (including dropouts)

The number and percentage of study participants who are absence seizure free based on diary will be summarized at 3-month time intervals within the Evaluation Period, as defined in [Table 3-3](#), and over the entire Evaluation Period truncated at the scheduled Month 24 YEV for participants who continue in the study beyond 2 years. The latter will additionally include any diary entries collected from the end of Months 22 to 24 up to the Month 24 YEV. The derivation of absence seizure freedom based on diary is specified in [Section 3.13.4](#).

Study participants who discontinue during or prior to each 3-month period and do not meet Criterion 1 are imputed as not absence seizure free for the period of discontinuation and all subsequent 3-month periods, ending at Months 22 to 24. These participants will be separately summarized as a sub-category of not absence seizure free in the summaries.

Similarly, study participants who discontinue during the Evaluation Period and do not meet Criterion 1 are imputed as not absence seizure free for the Evaluation Period; these participants will be summarized in a sub-category as described above.

The number and percentage of study participants who met each individual criterion will also be summarized. Percentages for absence seizure free, not absence seizure free and Criterion 1 will be based on the number of participants in the SS as the denominator. Percentages for criteria 2 and 3 will be based on the number of participants in the SS who met Criterion 1 at each visit.

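### In the including-dropouts diary analyses, the Evaluation Period row can count an early discontinuer as seizure free on diary data to the EDV, although SAP 4.1.1.1 describes nonresponse imputed to 24 months

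*SAP*

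**What the plan says.** - **Endpoint.** SAP 2.2.2 (Table 2-2) names diary-based freedom over the Evaluation Period, cut off at Month 24, as a secondary endpoint next to the 3-month intervals.
- **Length of the period.** Under SAP 3.3.2 the Evaluation Period runs to the FV, "or from the date of first dose in EP0132 until the EDV inclusive for study participants who prematurely discontinue the study". Table 3-2 agrees: "EDV inclusive for participants who discontinue the study early". If neither visit was attended, it ends on the last day of study medication.
- **Criteria.** SAP 3.13.4 sets three. Criterion 1 is "The study participant completed their seizure diary on at least 80% of days within the relevant period". The others are no absence seizure in the diary and no concomitant AED in the same period.
- **Discontinuers.** For a 3-month period in which someone leaves, 3.13.4 checks Criterion 1 against the full period. For the Evaluation Period it says only: "Study participants who discontinue the study early will still be included in the analysis conducted on the Evaluation Period".
- **Summary rule.** SAP 8.1.3 says that "study participants who discontinue during the Evaluation Period and do not meet Criterion 1 are imputed as not absence seizure free for the Evaluation Period". On the denominator, the same section reads: "not absence seizure free and Criterion 1 will be based on the number of participants in the SS as the denominator". That rule also covers the percentage counted as free.
- **50% version.** In SAP 3.13.6, "Criterion 1 will be updated to require a minimum of 50% of days of seizure diary completion within the relevant period"; the rest follows 3.13.4. SAP 8.1.7.1 uses the same denominator but has no sub-category for imputed discontinuers.
- **Overview.** SAP 4.1.1.1 says that EEG, diary and modified diary each have "one analysis with imputation of non-response truncated at 24 months for participants who discontinue the study early", and one without such imputation.

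**The concern.** A reader of 4.1.1.1 would expect every early discontinuer to be a nonresponder out to 24 months in the including-dropouts results. The Evaluation Period row does not do that. It shortens the period to the participant's own follow-up and imputes only when Criterion 1 fails, so a few clean weeks before leaving count the same as 24 months of freedom.

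The row also sits apart from neighbouring rules. The EEG analysis including dropouts (SAP 3.13.2) imputes nonresponse at every scheduled visit after the EDV to Month 24. The cumulative diary analysis (SAP 3.13.9) makes discontinuers nonresponders in all later 6-month periods whatever their status at the EDV. At stake is the reported percentage for a named secondary endpoint. The sub-category in 8.1.3 shows only discontinuers who fail Criterion 1, so it does not show those counted as free.

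**Working it through.** The plan has no figure of its own to reproduce: it gives no sample size calculation and no discontinuation rate. The check applies the written rules to one participant.

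**Inputs.** 3-month periods are 90 days, eight of them covering Days 1 to 720 (SAP 3.3.3, Table 3-3). The Evaluation Period ends at the EDV (Table 3-2). Criterion 1 is 80% (3.13.4) or 50% (3.13.6). N is about 140 (SAP 2.4). The participant has a complete diary, no absence seizure and no AED up to an EDV on Day d.

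**Evaluation Period row.** Completion = d/d = 100%, so Criterion 1 is met, nothing is imputed and the participant is free.

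**3-month rows.** Completion in the period of discontinuation = (diary days in that period)/90. Later periods have no diary days within the Evaluation Period and fail.

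| EDV day | Evaluation Period row | Period of discontinuation | 3-month rows not free |
|---|---|---|---|
| 30 | 30/30, free | Months 1 to 3: 30/90 = 33.3% | 8 of 8 |
| 200 | 200/200, free | Months 7 to 9: 20/90 = 22.2% | 6 of 8 |
| 400 | 400/400, free | Months 13 to 15: 40/90 = 44.4% | 4 of 8 |

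All three percentages are below 50%, so the 50% version gives the same counts.

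**Cut-offs.** Passing Months 1 to 3 needs 0.8 × 90 = 72 days (0.5 × 90 = 45 in the 50% version). An EDV before that day fails all eight rows whatever the diary shows. Passing Months 22 to 24, which start on Day 631, needs an EDV on or after Day 630 + 72 = 702 (630 + 45 = 675). Earlier discontinuers can still be free on the Evaluation Period row.

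**Alternative reading.** A fixed 720-day denominator is not stated for this row and conflicts with Table 3-2. It would not give full imputation either: a complete diary would pass from Day 0.8 × 720 = 576, or Day 0.5 × 720 = 360 in the 50% version.

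**Size.** Each discontinuer counted as free adds 1/140 = 0.71 points. In total this is q × s, where q is the share discontinuing and s the share of those free to the EDV. The documents give neither, so these values are assumptions:

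- q = 10%, s = 10%: 1 point (1.4 of 140)
- q = 25%, s = 20%: 5 points (7 of 140)
- q = 40%, s = 50%: 20 points (28 of 140), an upper end

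**The case against.** The strongest reply is that 4.1.1.1 is an overview that defers to 3.13.2 to 3.13.7 for the derivations. Its mention of 24 months fits the rule for later 3-month periods, and 8.1.3 states the Evaluation Period rule explicitly, so the row may be intended. The diary estimand does not list discontinuation as nonresponse, and protocol 9.6 evaluates discontinuers on the data collected. All of this is fair. It means that the fix is a change of rule to be declared, and that editing one sentence of 4.1.1.1 would remove the textual mismatch. It does not change what the row reports: a short-follow-up dropout can be a success in a table whose later rows call the same person a nonresponder.

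Other points that stand:

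- A strict result is partly available. The cumulative diary analysis (3.13.9, 8.1.6) treats discontinuers as nonresponders in later periods over the Safety Set, but it ignores AED use and so cannot replace this endpoint. The Months 22 to 24 row does include the AED criterion, but it covers one interval only.
- Discontinuers counted as free are not hidden. They can be found by subtracting the 8.1.4 count, or from the diary and disposition listings (SAP 8 and 5.1.1).
- Participants with an early FV can also be free on less than 24 months of diary. They are completers under SAP 3.3.5 and 4.1.1.1 does not cover them, so reclassifying discontinuers leaves that part of the short-follow-up problem in place.

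**Conclusion.** The point holds for two rows: the Evaluation Period row of 3.13.4/8.1.3 and that of 3.13.6/8.1.7.1. There, an early discontinuer who meets the criteria to the EDV counts as absence seizure free, which matches neither the description in 4.1.1.1 nor the 3-month rows of the same table. That follows from the text alone. The per-participant size of about 0.7 points rests on the approximate N of 140. The range of 1 to 20 points rests on assumed rates and shows what is possible, not what is expected.

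Three stronger readings are tempting but unsupported:

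- *All discontinuers are counted as successes.* Those with poor diary completion, an absence seizure or AED use before the EDV are already nonresponders.
- *The diary analysis is lenient throughout.* The 3-month rows after discontinuation are nonresponse, and the excluding-dropouts analysis of the Evaluation Period removes discontinuers (which is not the same as counting them as nonresponders).
- *The estimand is breached.* Neither it nor protocol 9.6 requires discontinuation to be nonresponse.

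The study is descriptive, with no hypothesis test, so no formal inference is affected. The change is worth making because the endpoint is a named secondary one and the remedy is small.

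**What to change.** On the Evaluation Period row in SAP 3.13.4, 3.13.6, 8.1.3 and 8.1.7.1:

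1. Classify participants who discontinue early before the Month 24 YEV as not absence seizure free, regardless of Criterion 1.
2. Show them in the imputed sub-category that 8.1.3 already has, and add that sub-category to 8.1.7.1.
3. Record the change in SAP 3.12, since it adds a nonresponse rule that the estimand and protocol 9.6 do not contain.
4. Keep the present to-EDV result as a supplementary row labelled as seizure free while in the study.
5. Leave early-FV completers under the current rule, and footnote how many are counted as free with less than 24 months of diary.

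The cost is wording in four sections, one entry in 3.12, one derivation flag and a footnote, with no new data. The downside is that the reported percentage may be lower.

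If the sponsor prefers the present rule, the minimum is to reword 4.1.1.1 so that it agrees with 8.1.3, and to report beside each of the two rows the number of discontinuers counted as free.

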3.3.3 Three- and six-month periods

A month is defined as 30 days and time intervals based on monthly durations are defined as a multiple of 30 days. The definitions of 3- and 6-month periods are described in [Table 3-3](#) and [Table 3-4](#) respectively.

Table 3-3: Definition of each 3-month period

Period	Days relative to date of first dose in EP0132
Months 1 to 3	1 to 90
Months 4 to 6	91 to 180
Months 7 to 9	181 to 270
Months 10 to 12	271 to 360
Months 13 to 15	361 to 450
Months 16 to 18	451 to 540
Months 19 to 21	541 to 630
Months 22 to 24	631 to 720
Months 25 to 27*	721 to 810
Months 28 to 30*	811 to 900
Months 31 to 33*	901 to 990
Months 34 to 36*	991 to 1080

Table 3-3: Definition of each 3-month period

Period	Days relative to date of first dose in EP0132
...	...

* These 3-month periods are only applicable for a subset of participants who remain in the EP0132 study past Month 24.

Table 3-4: Definition of each 6-month period

Period	Days relative to date of first dose in EP0132
Months 1 to 6	1 to 180
Months 7 to 12	181 to 360
Months 13 to 18	361 to 540
Months 19 to 24	541 to 720
Months 25 to 30*	721 to 900
Months 31 to 36*	901 to 1080
...	...

* These 6-month periods are only applicable for a subset of participants that remain in the EP0132 study past Month 24.

Three-month periods will be utilized for summaries and analyses of efficacy based on seizure data (diary data), AEs, and other safety endpoints. Six-month periods will be utilized for efficacy analyses of seizure data based on EEG, and consecutive and cumulative consecutive absence seizure freedom based on seizure data (EEG and diary data). For the analysis of AEs, participants will be included in 3-month period summaries if the end date of their Evaluation Period is on or after the first day of the 3-month period respectively.

Assessment visits are scheduled based on months calculated as 365.25/12 and thus are not fully aligned to the 3-month or 6-month periods described above. For example, the 7 to 12 month period would end at 360 days whereas the Month 12 visit is scheduled at 365 days. Similarly, the 19 to 24 month period would end at 720 days whereas the Month 24 visit is scheduled at 731 days. Further details are provided in [Table 3-5](#).

Table 3-5: Study periods vs scheduled assessments

Period	Days relative to date of first dose in EP0132	Scheduled assessment visit ^a	Scheduled assessment visit (days)
Months 1 to 3	1 to 90	MEV, Month 3	91

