If a study participant discontinues the study during a relevant period then Criterion 1 will be checked and if met, the participant will be assessed for absence seizure freedom in the period of discontinuation. If Criterion 1 is not met, then the status will be imputed as not absence seizure free for that specific period and for all subsequent 6-month periods (where applicable), ending at Months 19 to 24.

If a study participant has a FV during a relevant period then Criterion 1 will be checked and if met, the participant will be assessed for absence seizure freedom in the period of the FV. If Criterion 1 is not met, then the participant will not be included in the analyses for that specific period and for all subsequent 6-month periods (where applicable), ending at Months 19-24.

For the cumulative consecutive absence seizure freedom analysis, a study participant will be categorized as absence seizure free until the 6-month period in which they are first classified as not absence seizure free. After the recurrence of absence seizures, the participant is classified as not absence seizure free regardless of whether they met the criteria for absence seizure freedom in subsequent 6-month periods.

If a participant discontinues early, all subsequent 6-month periods for the participant are considered as not absence seizure free, regardless of their cumulative absence seizure status at the time of the EDV.

If a participant performs a FV before the end of the Month 19-24 period and becomes not absence seizure free at any point prior to or at the FV then the participant will remain in the analyses for subsequent 6-month periods as not absence seizure free. However, if the participant performs a FV before the end of the Month 19-24 period, and they remain absence seizure free until the FV, then they will remain in the analyses until the period of the FV if they met Criterion 1 during the period of the FV, or the period prior if they did not meet Criterion 1 during the period of the FV, and will be excluded from the analyses for all subsequent 6-month periods.

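### In the diary analyses that include dropouts, a participant whose Final Visit cuts a period short is left out of that period even when an absence seizure was recorded in it

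*SAP*

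**What the plan says.** SAP 3.13.4 sets three criteria for absence seizure freedom on diary in a 3-month period. They are a sufficiently complete diary (Criterion 1), no reported absence seizure (Criterion 2) and no concomitant AED (Criterion 3). Criterion 1 reads: "Seizure diary data is reported on the Seizure Classification eCRF for at least 80% of the days within the relevant period". The order is fixed: "Note that Criterion 2 and 3 will only be assessed if Criterion 1 is met". A participant who does not meet all criteria is otherwise not absence seizure free.

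Two kinds of exit get their own rule when Criterion 1 fails:

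- Early discontinuation: "If Criterion 1 is not met, absence seizure freedom status will be imputed as not absence seizure free for the period of discontinuation".
- Final Visit: "If a study participant has a FV during a 3-month period then Criterion 1 will be checked based on the full 3-month period", and then "If Criterion 1 is not met, the participant will not be included in the summary for that period and all subsequent 3-month periods".

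Section 3.13.6 takes over the whole derivation with a 50% threshold. Section 3.13.9 does the same for 6-month periods without Criterion 3, and says of an FV: "If Criterion 1 is not met, then the participant will not be included in the analyses for that specific period". Its cumulative version keeps in the analysis, as not seizure free, anyone who loses seizure freedom before or at the FV.

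Three other places bear on this. SAP Table 2-2 and Protocol Section 3 define both AED use and completion below 80% as nonresponse, with no FV exception. SAP 4.1.1.1 says the imputation analysis has no missing data, because anyone failing a criterion is not seizure free. SAP 8.1.3, 8.1.6 and 8.1.7.1 use the whole SS as denominator.

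**The concern.** One recorded absence seizure settles that the participant was not seizure free in that period, and no number of missing diary days can reverse it. For FV participants the record is never consulted, because completion is checked first against days that could not have been recorded after the FV.

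Three participants with the same diary (71 completed days of 90, one absence seizure) are therefore classified in two ways. The continuing participant and the early discontinuer are not seizure free, and the FV participant is left out. SAP 3.12, which lists changes to protocol-defined analyses, does not mention this departure from the estimand. FVs before Month 24 are foreseen: Protocol 4.1 has participants who move to another brivaracetam study, an access program or commercial drug complete an FV.

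**Working it through.** **Inputs.** Period lengths come from SAP 3.3.3 ("A month is defined as 30 days"), so 3 months = 90 days and 6 months = 180 days. The 80% threshold is from 3.13.4 and 3.13.9, and the 50% threshold from 3.13.6. Visit days are from SAP Table 3-5. Section 3.13.9 does not repeat that the check is on the full period, but it takes its derivation from 3.13.4, and I read it that way.

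**Days needed.** 0.8 × 90 = 72; 0.5 × 90 = 45; 0.8 × 180 = 144. An FV on day 71 or earlier of a 3-month period, or day 143 or earlier of a 6-month period, fails the 80% check even with a perfect diary.

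**Outcome when a seizure is recorded in a 3-month period (3.13.4).**

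| Status in period | 71 completed days | 72 or more |
|---|---|---|
| Continuing | not free | not free |
| Early discontinuation | not free | not free |
| Final Visit | left out | not free |

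Only one cell is out of line. The same holds for recorded AED use under Criterion 3.

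**Where an FV on a nominal visit day falls.** This assumes first dose on the Entry Visit day, because visits are counted from the Entry Visit and periods from first dose.

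| FV at | Day | Day of 3-month period (72 needed) | Day of 6-month period (144 needed) |
|---|---|---|---|
| Month 3 | 91 | 91 − 90 = 1 | 91 |
| Month 6 | 183 | 183 − 180 = 3 | 3 |
| Month 9 | 274 | 274 − 270 = 4 | 274 − 180 = 94 |
| Month 12 | 365 | 365 − 360 = 5 | 5 |
| Month 15 | 457 | 457 − 450 = 7 | 457 − 360 = 97 |
| Month 18 | 548 | 548 − 540 = 8 | 8 |
| Month 21 | 639 | 639 − 630 = 9 | 639 − 540 = 99 |
| Month 24 | 731 | after day 720 | after day 720 |

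Every nominal FV from Month 3 to Month 21 fails Criterion 1 in the period where it falls, including at the 50% threshold for 3-month periods. At most 9 days of 3-month diary are set aside. For 6-month periods, an FV at Months 3, 9, 15 or 21 sets aside 91 to 99 days. Within the ±7-day window a Month 24 FV falls on days 724 to 738, still after day 720.

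**Effect on percentages (illustration).** Take SS = 140, the planned enrolment. Assume 56 seizure free and k FV participants left out despite a recorded seizure. The documents give neither 56 nor k.

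- As written, not free = (140 − 56 − k)/140. For k = 3 this is 81/140 = 57.9%, and for k = 28 it is 56/140 = 40.0%.
- With the seizures counted, not free = 84/140 = 60.0%.
- Seizure free = 56/140 = 40.0% in every case.
- As written, the two categories sum to 97.9% (k = 3) down to 80.0% (k = 28).

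**The case against.** The strongest defence is that dropping administrative part-periods whatever their content is a coherent choice. The electroencephalogram (EEG) analyses in 3.13.2 and 3.13.3 likewise leave out visits after an early FV. Keeping only those part-periods in which a seizure occurred selects on outcome. If only included participants formed the denominator, that would bias seizure freedom downward. This part stands, and it limits where the fix should apply. It does not rescue the present rule in the SS-denominator tables, where the estimand calls for nonresponse and where counting these participants leaves the percentage seizure free untouched.

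The defence is also right that little is lost in most 3-month periods, that FV participants remain in the Evaluation Period analysis, and that all diary data are listed. The Evaluation Period ends at the FV, so truncation alone does not fail Criterion 1 there. The study is single-arm and descriptive, with no hypothesis testing.

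A reader might infer that early discontinuers lose recorded seizures too. In 3.13.4 and 3.13.9 they do not, because they are imputed as not seizure free. They leave only the versions built to omit dropouts, as in 3.13.5: "If they do not meet Criterion 1 during the period of study discontinuation the study participant will not be included in the analysis".

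A reader might also infer that 3.13.9 plainly overrides its own cumulative rule. The text does not go that far. The exclusion sentence can be read as governing the per-period analysis only. What is unclear is whether a seizure in an under-80% FV period counts as loss of seizure freedom, since Criterion 2 is not assessed there.

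**Conclusion.** The point holds for FV participants who fail Criterion 1 in the including-dropouts diary analyses (3.13.4, 3.13.6) and in 3.13.9. Their recorded absence seizures, and AED use where it is a criterion, are ignored in the FV period. The same diary from anyone else counts as nonresponse. This is inconsistent with the estimand and with 4.1.1.1, and it leaves the cumulative rule in 3.13.9 open to two readings.

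The effect is an understated percentage not seizure free and categories that do not add up to the SS. It is usually small for 3-month periods, larger for 6-month periods, and nil for an FV at the nominal Month 24 visit.

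Two stronger conclusions are tempting and unsupported. First, 71 of 90 days (79%) is the share of calendar positions at which an FV fails Criterion 1. It is not a share of participants, and the documents do not say how many FVs occur before Month 24. Second, the rule does not inflate the percentage seizure free in these tables, because the denominator is the whole SS. The conclusion rests on reading 3.13.9 as using the full 180 days and on first dose falling on the Entry Visit day.

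**What to change.** In SAP 3.13.4, 3.13.6 and 3.13.9:

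1. State that any absence seizure recorded in the period up to the FV, or AED use where Criterion 3 applies, makes the participant not absence seizure free for that period regardless of diary completion.
2. Limit the FV exclusion from that period to participants with neither, and say explicitly how later periods are handled for those with a recorded seizure. In 3.13.9, make the per-period and cumulative rules agree.
3. Keep the SS denominator in 8.1.3, 8.1.6 and 8.1.7.1, and show excluded FV participants as a separate row so that the categories sum to the SS.

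Leave 3.13.5 and 3.13.7 as they are, unless the denominators in 8.1.4 and 8.1.7.2 are amended at the same time. Their 3-month percentages are based on participants meeting Criterion 1, so counting others as not seizure free would place people outside the denominator.

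The cost is SAP wording, a change in derivation order and one table row, using data already on the Seizure Classification and Concomitant Medications eCRFs. The downside is a slightly higher reported percentage not seizure free.
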